The relationships that will be estimated for each mediator on each outcome are described in the primary mediation analyses, see “Mediation analyses”. The mediator models will be adjusted for the baseline score in the dependent variable (outcome), the mediator as well as the potential pre-treatment confounders. The interaction term between the intervention allocation and the mediator will be analysed to examine its impact on the indirect effects. The interaction term will be adjusted for in the outcome model if indicated. Missing data will be handled using full information maximum likelihood in the mediation analyses, if other methods are not indicated. The effects will be reported with 95% CI.

Predictors and sub-groups

-Baseline predictive factors

All baseline factors will be explored as potential predictors for health outcomes at time point 4 for the PainSMART intervention group cohort and also for the entire cohort. Regression based statistics will be used. Prediction models will be constructed exploring predictive performance. Internal and external validation of the models will be explored.

-Moderator analyses

Moderator analyses are planned based on the ÖMPSQ risk group categories. The two sub-groups are defined as high risk (score >50) and low risk (score ≤ 50) for persisting disability and work absence. The dependent variable is the intervention’s effect on health outcomes at time points 3 and 4.

Missing data

Proportion of missing and available data will be investigated through completion rate for each outcome measure and at all data collection time points. The proportion and patterns of missing data in outcomes will be assessed if missing data is $>5\%$. Comparison of characteristics and baseline score on PROMs between participants with and without missing data at one or several data collection time points or according to specific missing data patterns will be analysed to interpret the potential impact of missing data on generalizability.

Imputation will be conducted and handled under the missing at random assumption. In the event of substantial missing data, an evaluation of the mechanisms for missing data will be conducted (Enders, 2011). Multiple Imputation or Restricted Maximum Likelihood estimation will be used assuming that missing data is conditional on variables included in the model. Other imputation methods may be used if necessary.

[Statistical software](#)

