Communication between people with MSKP and healthcare practitioners can be difficult and may be hampered by a divergence in understanding and expectations between the healthcare practitioner and the patient (Parsons et al., 2007). For example, qualitative evidence consistently finds that people with MSKP want definitive diagnoses and an explanation of the cause of their pain (Lim et al., 2019; Toye et al., 2013; Verbeek et al., 2004). However, as MSKP is considered an emergent neurophysiological phenomenon explaining it can be complex and providing a definitive diagnosis is often impossible (Moseley & Butler, 2017; O'Sullivan et al, 2019). A divergence in expectations can therefore arise in a clinical consultation when, for example, a physiotherapist approaches MSKP as a complex emergent phenomenon and a patient views MSKP through a traditional biomedical lens. Indeed, a patient's lack of knowledge or their uncertainty about their condition has been shown to hinder effective consultations and the implementation of evidence-based healthcare (Correa et al., 2020; Parsons et al., 2007). An idealistic strategy may be that educational interventions are administered prior to a healthcare consultation to help reduce divergence in understanding between a patient and healthcare practitioner by providing a shared basis for communication. The PainSMART-strategy has been developed in part to address such divergences in

understanding. It is hoped that the implementation of the PainSMART-strategy may facilitate patient-practitioner interaction around MSKP and result in improved patient outcomes compared to usual healthcare management.

Objectives

The PainSMART-project is a research program with a collective suite of studies aiming to investigate the effectiveness of the PainSMART-strategy, factors associated with outcomes and explore patients and physiotherapists experiences. The objective of the PainSMART-project is to evaluate the effects of administering the PainSMART-strategy as an adjunct to usual physiotherapy management compared to usual physiotherapy management alone.

Hypotheses

Hypotheses for confirmatory research questions:

1. Exposure to the PainSMART-strategy as an adjunct to usual physiotherapy management improves the following outcomes significantly more than usual physiotherapy management alone for patients with MSKP (* = primary outcomes)
 - Reduction in pain intensity*.
 - Higher pain self-efficacy*.
 - Lower MSKP illness perceptions.

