This statistical analysis plan is part of the PainSMART-project which is a collective suite of studies utilising mixed methods. The PainSMART-project was initiated in 2021 with the aim of improving early musculoskeletal pain (MSKP) management through patient-centered MSKP education based on modern pain science. The PainSMART project's motivation is the high burden of MSKP and the issues encountered within primary care clinical practice associated with the persistence of misconceptions surrounding MSKP. The PainSMART-project has to date conducted pilot-studies within the primary care setting that have led to the development of the seven-minute-long digital educational film entitled 'Be PainSMART:er' (hereafter known simply as 'the film'). The film forms the basis for the implementation of a two-stage PainSMART-strategy which consists of exposure to the film prior to the initial physiotherapy consultation and a discussion based on the film between the patient and the physiotherapist at the initial physiotherapy consultation. The aim of this study is to scientifically evaluate the effects of adding the PainSMART-strategy to the current MSKP primary care physiotherapy care pathway in the Swedish healthcare regions of Östergötland (RÖ) and Jönköping (RJL).

Description of specific objectives or hypotheses

The objective of the PainSMART-project is to evaluate the effects of administering the PainSMART-strategy as an adjunct to usual physiotherapy management compared to usual physiotherapy management alone.

Research hypotheses for confirmatory research questions

1. Exposure to the PainSMART-strategy as an adjunct to usual physiotherapy management improves the following outcomes significantly more than usual physiotherapy management alone for patients with MSKP (* = primary outcomes) (H1)

- Reduction in pain intensity*.
- Higher pain self-efficacy*.
- Lower MSKP illness perceptions.
- Higher levels of reassurance of the benign nature of MSKP.
- More adaptive MSKP coping and psychological flexibility.
- Higher self-reported levels of physical activity.
- More positive global ratings of change.
- Lower number of healthcare visits, referrals for diagnostic imaging and to specialist/tertiary care for MSKP, lower analgesic medication use, fewer sick leave days and lower direct costs.

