- More positive and concordant patient and physiotherapist evaluations of MSKP-related shared understanding, communication, participation, involvement and emotional support at the initial physiotherapy consultation.

2. Improvements in MSKP illness perceptions and higher levels of reassurance of the benign nature of MSKP mediate improved pain intensity and pain self-efficacy as a result of exposure to the PainSMART-strategy compared to usual physiotherapy management alone.

The null hypothesis (H0) is that there is no clinically or statistically significant differences between the intervention (film) group and the control group (usual physiotherapy management).

Secondary exploratory research questions

1. What baseline factors are predictive of improved patient outcomes after exposure to the PainSMART-strategy?
2. What baseline factors are predictive of the persistence of MSKP?
3. What type of psychological factors and strategies are associated with patient outcomes after exposure to the PainSMART-strategy?
4. Is pain self-efficacy a potential mediator of the PainSMART-strategy's effect on health outcomes?
5. What are patients and physiotherapists experiences of the PainSMART-strategy?

Study Methods

Trial design

This is a two-armed, parallel group, randomised controlled trial in which the intervention group (PainSMART-strategy + usual physiotherapy management) will be compared to a control group (usual physiotherapy management). Treatment allocation is a 1:1 ratio. The control group and statistician will be blinded. One independent statistician will be blinded for the primary analyses. Another independent statistician will be responsible for database development and linkage of patient and physiotherapist data. The PainSMART-strategy is described in full in the trial protocol.

Randomisation

A computerised randomisation sequence for 800 patients into group A (Intervention group) or B (Control group) has been generated by a blinded statistician using SPSS prior to the start of patient recruitment. Participating patients will be allocated to intervention or control group based on the order of their inception to the study. The randomisation is described in full in the trial protocol.

Framework

The trial's hypotheses apply a superiority testing framework where the PainSMART-strategy is hypothesized to be superior in outcome compared to control.

Determination of Sample size

The sample size calculation is described in full in the trial protocol.

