The study specific minimal clinical important differences (MCID) for primary outcomes at primary time points will be calculated for interpretation of the within and between-group differences. The MCIDs will be calculated for the whole cohort using an anchor method (Revicki et al, 2008). A dichotomised anchor response on the GRoC (-5- 0 = not improved; 1-5 = improved) must at least have a small association with change in the primary outcome baseline to primary time points one and two. This will be applied in a receiver operator characteristic (ROC) curve analysing the area under the curve (AUC), specificity, sensitivity and Youden index to attain an optimal cut off point for the MCIDs. MCIDs will be presented in mean and SD.

[Secondary outcome analysis](#)

[Patient reported outcome analyses](#)

-Continuous variables

Hypothesis testing for secondary outcomes for *pain intensity*, *pain self-efficacy*, *MSKP illness perceptions (BIPQ)*, *reassurance of the benign nature of MSKP*, *traditional pain coping strategies (BPCI-2, sub-scale for pain coping strategies)*, *psychological flexibility (BPCI-2 sub-scale for psychological flexibility)*, and *physical activity levels (moderate to intensive exercise, Other physical activity beside exercise, Sitting time)* will be based on analysis of group mean change from baseline. Baseline group mean scores and group mean change for each secondary outcome score from baseline to all time points for the intervention and control groups and the between-group mean change at all time points will be presented as means and CI. The within and between-group change on outcomes from baseline to 24-72 hours prior to the initial physiotherapy consultation, 24 hours post initial physiotherapy consultation and three months post-baseline will be analysed according to the ITT principle using a maximum likelihood approach for mixed models adjusted for a relevant covariance structure. The models will be adjusted for baseline covariates where relevant. Baseline factors that will be analysed for potential covariate adjustment include: age, sex, educational level, employment, pain duration, number of pain sites, comorbidities, days to initial physiotherapy consultation, previous health care interventions, ÖMPSQ risk category, self-reported sick leave and analgesic medication consumption.

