The study specific MCIDs for secondary outcomes at all time points will be calculated for interpretation of the within and between-group differences. The MCIDs will be calculated for the whole cohort using an anchor method (Revicki et al., 2008). A dichotomised anchor response on the GRoC (-5- 0 = not improved; 1-5 = improved) must at least have a small association with change in the secondary outcome from baseline to all time points. This will be applied in a ROC curve analysing the AUC, specificity, sensitivity and Youden index to attain an optimal cut of point for the MCIDs. MCIDs will be presented in mean and SD.

-Categorical variables

Hypothesis testing for secondary dichotomous outcomes for *Global rating of change*, *fulfilment of physical activity recommendation*, *analgesic medication consumption*, *self-reported sick leave* and *self-reported healthcare visits* will be based on analysis on differences in proportions over time using generalised linear mixed models. For the secondary multinomial outcome regarding *type of analgesic medications* (1. Paracetamol, 2. NSAID, 3. Opioids/gabapentinoids/Tricyclic antidepressants/Serotonin-norepinephrine reuptake inhibitors) differences in proportions over time will be analysed using generalised logit mixed models. The numbers and proportions for secondary dichotomous outcomes will be reported at all relevant time points for the intervention and control groups as well as between-group comparisons for all time points presented as odds ratio and CI.

Healthcare register outcome analyses

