Patients receive seven questions and physiotherapists 3 questions regarding their experience of the initial physiotherapy consultation. Between group mean difference for responses to these questions will be analysed using independent sample t-tests. These analyses will be presented as mean and SD for each group and the between group difference in mean and CI. Three of the patient questions will be analysed for concordance with the matched physiotherapists' questions. Concordance within the intervention group and control group will primarily be analyzed by calculating intraclass correlation coefficient (ICC) with 95% confidence interval on each question as well as all three questions combined. Two-way random effects model will be used for ICC, assuming raters to be randomly selected. The ratings are single measures analyzed for consistency, to measure systematic differences between ratings. Patients and physiotherapists are treated as two independent raters, rating each of the three questions.

Sensitivity analyses

The following are all re-analyses of the primary and secondary outcomes under different conditions:

- Per-protocol analysis
- Complier average causal effect (CACE) analysis
- Responder analysis
- Complete case analysis (in case of >5% missing data)

Per-protocol analysis

Per-protocol analyses for the primary and secondary outcomes will be conducted to assess robustness of the ITT analyses and to further inform decisions regarding superiority. The sample of the patients for the per-protocol analyses will be as follows:

- Intervention group: patients receiving the PainSMART-strategy with no or minor deviation from protocol.
- Control group: patients receiving intervention with no or minor deviation from protocol.

Data on the physiotherapists' self-reported adherence to the protocol will be cross-referenced with the intervention respective control group patient consultations that each physiotherapist has conducted. This, in combination with the intervention group patients' self-reported exposure to the film, will provide data on deviation from protocol.

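### Every secondary outcome sits in the same confirmatory hypothesis as the two primaries, with no order, gate or adjustment across outcomes

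*SAP*

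**What the plan says.** The SAP (Description of specific objectives or hypotheses) uses the heading "Research hypotheses for confirmatory research questions". The protocol (Hypotheses) has "Hypotheses for confirmatory research questions". Under both, hypothesis 1 states that the strategy "improves the following outcomes significantly more than usual physiotherapy management alone for patients with MSKP (* = primary outcomes) (H1"). An asterisk is the only thing that separates pain intensity and pain self-efficacy from the other entries. One bullet alone covers healthcare visits, "referrals for diagnostic imaging and to specialist/tertiary care for MSKP, lower analgesic medication use, fewer sick leave days and lower direct costs". Another covers "More positive and concordant patient and physiotherapist evaluations of MSKP-related shared understanding, communication, participation, involvement and emotional support". A separate list of questions is called exploratory.

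The SAP then specifies hypothesis tests:

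- **Continuous patient-reported outcomes:** mixed models, where "the between-group mean change at all time points will be presented as means and CI".
- **Categorical outcomes:** testing "will be based on analysis on differences in proportions over time using generalised linear mixed models".
- **Register outcomes and costs:** mixed models and a t-test respectively.
- **Consultation-experience items:** "Between group mean difference for responses to these questions will be analysed using independent sample t-tests".

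On error control, the SAP (Statistical Principles) sets alpha at 0.05 for one-sided tests and uses two-sided 95% confidence intervals. It declines adjustment across outcomes because they are treated as separate entities, and applies Bonferroni to repeated measures over time. The protocol (Multiplicity/type I error) takes the same position. Neither document gives a testing order, a gate or a familywise error rate.

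**The concern.** Leaving secondary outcomes unadjusted is ordinary practice when they are supportive. Calling outcomes confirmatory is also reasonable when error across them is controlled. This plan calls them confirmatory and declines any control across them, and the two choices do not fit together. Because the documents keep a separate exploratory list, the word confirmatory does real work in hypothesis 1.

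What is at stake is what may be claimed at the end. The analysis of the two primaries is not affected. But if they turn out null and one of a dozen or more secondary outcomes is significant, the text does not stop that result being reported as a confirmed hypothesis. The protocol (Dissemination) says the film can be built into the care pathway if results are positive, and does not define positive.

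**Working it through.** The documents state no familywise figure, so there is none to reproduce. The check counts the outcomes and then computes the chance of at least one false positive in the favourable direction when the strategy has no effect on any of them.

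**Count**

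- *Named in hypothesis 1, without the experience bullet: 12.* Seven are measured repeatedly: illness perceptions, reassurance, coping, psychological flexibility, physical activity, global rating of change and analgesic use. Five are totals over the study period: visits, imaging referrals, specialist/tertiary referrals, sick leave days and direct costs.
- *Analysed variables, without the experience items: 20.* Fifteen are patient-reported: worst pain, best pain, illness perceptions, reassurance, coping, flexibility, three activity items, the 150-minute threshold, global rating of change, analgesic consumption, analgesic type, sick leave and visits. The same five register or cost outcomes are added.
- *Left out of both counts:* the primaries, average pain and self-efficacy at time point 2, the ten experience items and their concordance analyses, and the eight mediator models.

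**Test levels**

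Each repeated outcome is tested at three time points at alpha/3. Each register or cost outcome is tested once at alpha. Alpha is 0.05 (one-sided rule) or 0.025 (a two-sided 95% interval excluding zero in the favourable direction).

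**Assumptions not in the documents**

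The correlation between time points within an outcome is 0.6. The correlation between outcomes is a common value rho from 0 to 0.8. All outcomes are scored so that positive is favourable.

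**Independent outcomes, by formula**

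Let p3 be the chance that a three-time-point outcome gives at least one positive at alpha/3. By simulation p3 is 0.0407 at alpha 0.05 and 0.0211 at alpha 0.025. Then P(at least one) = 1 − (1 − p3)^k3 × (1 − alpha)^k1.

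- 12 outcomes, 0.05: 1 − 0.9593^7 × 0.95^5 = 1 − 0.7476 × 0.7738 = 42%
- 20 variables, 0.05: 1 − 0.9593^15 × 0.95^5 = 1 − 0.5362 × 0.7738 = 58 to 59%
- 12 outcomes, 0.025: 1 − 0.9789^7 × 0.975^5 = 1 − 0.8613 × 0.8811 = 24%
- 20 variables, 0.025: 1 − 0.9789^15 × 0.975^5 = 1 − 0.7262 × 0.8811 = 36%

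**Correlated outcomes, by simulation**

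At each time point the test statistic is sqrt(rho) × G + sqrt(1 − rho) × E, with G shared by all outcomes and E specific to each. There were 200,000 runs per setting.

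| Set | Alpha | rho 0 | rho 0.5 | rho 0.8 |
|---|---|---|---|---|
| 12 named outcomes | 0.05 | 42% | 27% | 17% |
| 20 variables | 0.05 | 58% | 33% | 20% |
| 12 named outcomes | 0.025 | 24% | 16% | 10% |
| 20 variables | 0.025 | 36% | 21% | 12% |

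At alpha 0.05 the expected number of false-positive outcomes is 7 × 0.0407 + 5 × 0.05 = 0.53 for the 12, and 15 × 0.0407 + 5 × 0.05 = 0.86 for the 20.

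**Sensitivity**

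- The protocol tests the register outcomes once, by t-test. The SAP puts four of the five into mixed models at three time points. With those four at alpha/3, the one-sided 0.05 results at rho 0.5 become 25% and 32%.
- Adding the ten experience items as single tests to the 20 variables gives 41% at rho 0.5 (23% at 0.8, 75% if independent).
- Twenty single independent tests at 0.05 would give 1 − 0.95^20 = 64%. That ignores both the Bonferroni step over time points and any correlation, so it is an upper reference only.

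**The case against.** Several points on the other side are sound. The documents keep primary and secondary outcomes apart through asterisks, separate headings and a sample size built on the primaries. Declining adjustment across outcomes is a disclosed and referenced choice, not an oversight. The null hypothesis also refers to clinical relevance, and study-specific minimal important differences are planned for interpreting the continuous secondary measures.

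A reader might also infer more than the text supports:

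- *That one significant secondary result would count as trial success with both primaries null.* No passage says so. The text only fails to exclude it.
- *That the plan breaks a promised 5% familywise rate.* The 0.05 is a nominal level per test, and no familywise rate is promised.
- *That each outcome is tested at full alpha at every time point.* Bonferroni over time holds each repeated outcome at or below 0.05.
- *That 20 secondary hypotheses are listed.* Hypothesis 1 names about 12 plus the experience items. Worst and best pain and sitting time, for example, enter only as analysed variables.
- *That a chance finding would lead to roll-out.* The Dissemination section says only that the film can be integrated, and ties this to no particular outcome.

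These points limit the size of the problem and what can be said about intent. They do not remove the conflict between the confirmatory label and the absence of any control across the outcomes that carry it.

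**Conclusion.** The point holds as a defect of labelling and claim rules. Following the plan as written, a secondary result that arose by chance may be called a confirmed hypothesis. At a between-outcome correlation of 0.5 the probability of at least one such result, with no true effects, lies between about 16% (12 named outcomes, interval rule) and 33% (20 variables, one-sided 0.05). Over correlations from 0.8 to 0 the full span is 10% to 58%.

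No single figure should be quoted without its assumptions. The correlation is assumed, the count depends on whether named outcomes or analysed variables are used, and the SAP does not say whether the one-sided test or the two-sided interval decides a secondary claim. Every combination examined exceeds 5%. The experience items and mediator models would add to the count.

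**What to change.** In the protocol (Hypotheses) and the SAP (Description of specific objectives or hypotheses), keep confirmatory in hypothesis 1 for the two starred primaries only. Label the remaining outcomes in hypothesis 1 secondary and supportive: reported as estimates with confidence intervals, with no claim of a confirmed effect, and read in the light of the primary result.

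Treat hypothesis 2 and the eight mediator models in the SAP (Mediation analysis, Table 1) in the same way, or state why they stay confirmatory.

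If the sponsor wants confirmatory secondary claims, name a short fixed sequence, for example illness perceptions and then reassurance, which follows the plan's own proposed mechanism. Such a sequence needs a gate. The SAP must therefore first define what counts as success on two primaries at two primary time points.

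The cost is wording in two documents. No data, planned analysis or sample size changes. The downside is that a lone significant secondary outcome can no longer be called confirmed.
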